### 3.0 Study Outcomes

- 3.1 Primary Outcome: The primary outcome of this feasibility trial will be to determine if infants randomized to the enhanced nutrition protocol receive higher amounts of calories and protein throughout the first week of hospitalization.
- 3.2 Secondary Outcomes: The secondary outcomes will include measures of growth, neurodevelopment and growth hormone levels. Specifically, we will examine growth, not only in weight and length, but also in different compartments (FFM and FM) using weekly ADP measurements. We will also continue to track gains in these compartments beyond hospital discharge until 4 months CA. For neurodevelopment, we will utilize ERP techniques to look specifically at the effects of early enhanced nutrition on neural speed of processing and early cognition. Finally, we will look at the effect of early enhanced nutrition on IGF-1 and IGF-BP3 levels.

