Markers of Growth hormone axis activity (Outcomes for Aim 3): IGF-1 and IGFBP3 levels will be obtained in serum at 1 week of age and ~35 weeks CA. These specific markers were chosen as associations have been seen between linear growth, FFM gains, metabolic risk (e.g. increased adiposity and higher blood pressure), neurodevelopmental outcomes and IGF-1 and IGFBP3 in preterm born infants . IGF-1 and IGFBP3 will be analyzed by the Fairview Clinical Laboratory.

Additional Measures: The randomized design of this trial is expected to make the distribution of potential confounder values and characteristics similar in the intervention and control groups. Nonetheless, to confirm their equivalence and to describe the study sample, we will obtain birth anthropometrics, maternal age, education, and ethnicity, infant sex, gestational age at birth, weight-for-age z score at birth, and degree of illness from the medical record or parental self-report at enrollment. Degree of illness will be assessed using the Score for Neonatal Acute Physiology (SNAP) on DOL#1, 7, 14 and  $21^{34-35}$ . We will also collect data on other non-specific markers of illness, including days on the ventilator, requirement for blood pressure support, sepsis evaluations and antibiotic therapy, steroid administration, necrotizing enterocolitis (NEC), diagnosis of chronic lung disease and retinopathy of prematurity (ROP) etc. These measures will also allow us to track the safety of the intervention to ensure that rates of these common morbidities are similar in both groups.

5.3 Storage and Access: The records of this study will be kept private. In any publications or presentations, we will not include any information that will make it possible to identify the mother or baby as a subject. Any hard copies of the baby's research records will be kept in a locked desk in the locked office of the PI, co-I or study coordinator, and will be identified ONLY by an assigned study ID number (other identifying information will be removed). The study information will not be recorded in the medical record. These de-identified data will be entered into electronic format for storage and analysis; only the PI, co-Is, study coordinators and data analyst will have access to this electronic dataset.

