#### 16.0 Data Management

15.1 Data Analysis Plan: Data from the various domains will be entered by the study personnel into a web-based secure database (RedCap) for storage, retrieval and analysis. The NICU dietician is responsible for abstracting nutritional data from the electronic medical record (Epic). ADP data will be entered into the database by the study coordinators. ERP data will be abstracted by [name] and cleaned of artifacts as previously described. The data analyst will examine each variable for outliers and distributional properties and flag and correct entry errors where possible

and will log-transform or otherwise normalize variables prior to analysis. From RedCap all datasets will then be securely stored using Box.com per the HRPP policy. They may need to be downloaded to University/AHC desktops for statistical analysis, however only a subset of the team will be given access to all files (study coordinator and PI) and the rest will have access to the de-identified files only. These laptops are password protected and maintained by the AHC. Although we do not anticipate many missing values in this short-term follow-up study, multiple imputation methods (e.g., Proc MI in SAS) will be used if missing data can reasonably be considered missing at random. Analyses will also be run without imputation and results compared. Analyses will be carried out using SAS version 9.4 (SAS Institute Inc.) using an intent-to-treat approach, with a 2tailed p<0.05 as the threshold for statistical significance. For Specific Aims 1, 2, and 3, body composition data, neurodevelopmental outcomes, and IGF-1 and IGFBP3 will be treated as continuously-distributed variables assessed at multiple time points. For the ERP outcomes (which are measured twice), the primary hypotheses will be addressed using a simple general linear regression model for term-equivalent measures, and another similar model for 4 month corrected age measures, with assigned group as the independent variable in both cases. For FFM (with up to 10 repeated measures) and IGF-1 models, mixed effects regression models (using

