PROC MIXED) will be used. The primary models will test assigned group (standard versus enhanced nutrition protocol) and assigned group x time interaction as the tests of differences in the group mean values for initial levels, and change over time, respectively, between intervention and control groups. To improve the precision of estimates, variables of interest (e.g., gestational age at birth, anthropometric z scores at birth, degree of illness, etc.) will be included in additional, secondary models. In addition, in Specific Aim 3, IGF-1 levels at both 1 week and 35 weeks will be examined as predictors of later neurodevelopment and body composition outcomes. IGF-1 will be considered a potential mediator of the intervention-outcome relationships if 1) the intervention is significantly associated with both IGF-1 levels and outcomes, 2) IGF-1 levels are significantly associated with FFM and neurodevelopmental outcomes, and 3) in a model that includes both IGF-1 and treatment group as predictors. the effect of treatment group on outcomes (mean differences) is diminished compared to results from models unadjusted for IGF-1. Other ways of assessing the possible role of IGF-1 in the treatment-outcome relationship will also be explored.

15.2 Power Analysis: A sample size of 40 infants in each treatment group (80 total) allows for up to a ~12% loss to follow-up after discharge and still have 35 infants per group. Our prior work showed a significant association of early nutrition (protein and calories in first week of life) with FFM gains throughout hospitalization (p<0.01 for both) in 34 VLBW preterm

> infants. We have also shown that higher energy (kcal/kg/day) across hospitalization was associated with faster speed of processing (shorter latency) in 16 preterm subjects. We therefore expect that this pilot study, which is 2-3 times as large as previous studies, will be sufficient to produce statistically significant differences between groups. As this is a pilot trial, however, we have not conducted a formal power calculation. Rather, the results of this pilot exploratory study will generate estimates of effect size that will then be used to calculate sample size for our planned larger trial.

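### The primary fat-free mass model omits birth weight z score, a pre-randomisation variable in hand for every infant, so precision is lost on the group difference in level

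*Combined protocol and SAP*

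**What the plan says.** The Data Analysis Plan (15.1, under section 16.0) specifies mixed models for FFM, with up to 10 repeated measures, and for IGF-1: "The primary models will test assigned group (standard versus enhanced nutrition protocol) and assigned group x time interaction". The group term is described as the test of initial levels and the interaction as the test of change over time. No covariate is named. The next sentence gives precision as the reason for adjusting, offers gestational age at birth as its first example, and continues: "anthropometric z scores at birth, degree of illness, etc.) will be included in additional, secondary models".

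On what is available, section 5.2 (Additional Measures) states: "we will obtain birth anthropometrics, maternal age, education, and ethnicity, infant sex, gestational age at birth, weight-for-age z score at birth". Degree of illness is measured by SNAP on days of life 1, 7, 14 and 21. Section 9.1 requires a birth weight below 1500 g. Section 4.1 places randomisation after consent and NICU admission, stratified by gestational age in three bands.

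On size and purpose, the Power Analysis (15.2) says "A sample size of 40 infants in each treatment group (80 total) allows for up to a ~12% loss to follow-up after discharge". It puts the remaining number at 35 per arm. Because this is a pilot, it adds, "we have not conducted a formal power calculation". The results are meant to supply effect sizes for a larger trial. The primary outcome in section 3.1 is first-week calorie and protein intake; growth and body composition are secondary (3.2).

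**The concern.** FFM has no pre-treatment value. Section 5.2 starts body composition measurement once the infant is stable and tolerates room air, whereas the enhanced protocol starts as soon as there is IV access. Birth weight z is the natural pre-randomisation stand-in for starting size. It is known for every enrolled infant, because birth weight decides eligibility and randomisation comes after birth.

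Without it, between-infant differences in starting size stay in the error of the level contrast. Any treatment effect that builds up before the first measurement also falls in that contrast. In a pilot with no power calculation, whose product is effect-size estimates, that precision matters.

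The planned secondary models are not a clean substitute. Their covariate list is open, and it includes degree of illness. SNAP on days 7, 14 and 21 is post-randomisation and could be affected by the nutrition under test, so a model containing it answers a different question from one adjusted for birth size alone.

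**Working it through.** **The plan's own figure.** 40 x (1 - 0.12) = 35.2, so 35 per arm after about 12% loss reproduces (5/40 = 12.5%). There is no stated power, effect size or SD to check.

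**Inputs.** From the documents: 35 per arm and "2tailed p<0.05 as the threshold for statistical significance". Assumed, because the documents give no value: the correlation r between birth weight z and later FFM z, taken as 0.3, 0.5 and 0.6.

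**Level or single-visit contrast.**
- Unadjusted 95% half-width = t(0.975; 68 df) x sqrt(2/35) = 1.995 x 0.239 = 0.477 SD.
- Adjustment multiplies the standard error by sqrt(1 - r^2), which acts like 1/(1 - r^2) times as many infants.

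| r | SE factor | Reduction | Effective n factor | Half-width (SD) |
|---|---|---|---|---|
| 0 | 1.000 | - | 1.00 | 0.48 |
| 0.3 | 0.954 | 5% | 1.10 | 0.46 |
| 0.5 | 0.866 | 13% | 1.33 | 0.41 |
| 0.6 | 0.800 | 20% | 1.56 | 0.38 |

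Charging one degree of freedom multiplies the SE by sqrt(68/67) = 1.007, giving factors of 0.961, 0.872 and 0.806. The difference detectable with 80% power is (1.960 + 0.842) x 0.239 = 0.67 SD unadjusted, and 0.64, 0.58 or 0.54 SD adjusted. At the full 40 per arm, which is nearer the inpatient number, it is 0.63 SD unadjusted and 0.60, 0.55 or 0.50 SD adjusted.

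**The repeated-measures model.** Take balanced data with 6 visits (t = 0 to 5), a random intercept (SD 1), a random slope (SD 0.15) and residual SD 0.4. All of these are assumptions. The variances of the group differences in level and slope are then (2/n) times the diagonal of D + 0.16 x (Z'Z)^-1. Here D is the random-effects covariance, and the diagonal of (Z'Z)^-1 is 55/105 = 0.524 and 6/105 = 0.0571.

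- *Level, r = 0.5 with the intercept.* Unadjusted: 1 + 0.16 x 0.524 = 1.084. Adjusted: 0.75 + 0.084 = 0.834. SE ratio sqrt(0.834/1.084) = 0.877, close to the single-visit 0.866.
- *Slope, birth z as a main effect only.* A covariate coefficient that is constant over time does not alter the slope variance in D. The SE ratio is 1.00.
- *Slope, birth z x time added.* Unadjusted: 0.0225 + 0.16 x 0.0571 = 0.0316. If birth z is uncorrelated with the slope, the ratio is 1.00. At a slope correlation of 0.3: 0.0225 x 0.91 + 0.0091 = 0.0296, ratio 0.97. At 0.5: 0.0225 x 0.75 + 0.0091 = 0.0260, ratio 0.91.

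The gain is therefore mainly in level. For change it runs from nil to about 9% in the cases tried, and only if birth size predicts the slope.

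**The case against.** The strongest objection is that Aim I is indexed by FFM gains, which the plan tests by group x time, and a birth-size main effect does nothing there. That stands. A reader might infer that the 5% to 20% reductions apply to FFM gain, or that gain cannot be judged without a starting size. Neither holds: change is estimated from repeated values on the same infants, and stable size differences enter mainly the level contrast. The point survives because level is the other declared primary test.

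Four further readings are tempting, and the documents do not support them.

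- *That adjustment is optional, or may never be done.* The plan commits to the secondary models. Their weakness is the open, mixed covariate list and their subordinate place.
- *That the unadjusted estimates are biased.* Randomisation protects them; only precision is affected.
- *That the primary weight, length and head circumference models share the fault.* Section 3.2 lists weight and length among the outcomes, but section 16.0 describes models only for FFM, IGF-1 and the ERP measures.
- *That every birth measurement is available before randomisation in every infant.* The documents show this for birth weight alone. For birth length and head circumference they give neither completeness nor timing relative to randomisation.

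It is also fair to say that the size is assumed. FFM will be analysed as reference z scores, and how well birth weight z predicts them, particularly at 4 months corrected age, cannot be known from these documents. At r = 0.3 the half-width moves only from 0.48 to 0.46 SD.

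**Conclusion.** The point holds for the FFM level contrast. The primary model leaves out a pre-randomisation variable that is known for every infant, already collected, and of a kind the plan itself credits with improving precision. For assumed correlations of 0.3 to 0.6, the cost is a standard error that adjustment would cut by about 5% to 20% at a given visit. For the FFM gain contrast the cost is between nothing and a few per cent, up to about 9% in the most favourable case tried, and a time interaction is needed to recover it. These figures rest on the assumed correlations and variance components, balanced data, and 35 infants per arm.

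The consequence is moderate. FFM is a secondary outcome of a feasibility pilot whose primary outcome is nutrient intake. What suffers is the precision of the effect sizes carried forward to the next trial, not the validity of the comparison.

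**What to change.** In section 16.0 (15.1), before any comparison by group:

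1. Pre-specify birth weight z score and its interaction with time as covariates in the primary FFM model, and in the FM model if FM is modelled the same way.
2. Keep the model with group and group x time but no birth-size terms as a sensitivity analysis.
3. Leave post-randomisation illness measures, including SNAP on days 7, 14 and 21, out of the primary model.
4. Do not word the change so that it bars gestational age, which is the stratification factor.
5. If weight, length or head circumference are modelled, use the matching birth z score where it was recorded before randomisation.

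The cost is SAP wording and two model terms. No new data are needed for FFM, since the birth weight z score is already collected.

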### 1.0 Objectives

1.1 The overall objective of the proposal is to demonstrate the feasibility of providing increased calories and protein in the first week of life to VLBW preterm infants, and to generate pilot data on the effects of this intervention on growth and neurodevelopmental outcomes. We hypothesize that infants receiving greater calories and protein in the first week of life will have improved FFM gains and higher levels of IGF-1 prior to discharge, and improved early cognition and faster speed of neural processing measured at term and 4 months corrected age (CA). To address these hypotheses, we propose the following specific aims:

Specific Aim I. Examine whether infants receiving earlier initiation of intralipids and more rapid increases in energy and protein intake during the first week of life ("enhanced nutrition protocol") have improved growth, indexed by increased FFM gains, compared to a standard nutrition protocol. Body composition will be measured weekly using air displacement plethysmography (ADP) until discharge and at term and 4 months CA.

Specific Aim II. Determine if infants on the "enhanced nutrition protocol" have improved cognition and faster speed of processing at term and 4 months CA compared to a standard nutrition protocol. Neurodevelopmental outcomes will be measured using electrophysiologic (ERP) techniques.

Specific Aim III. To assess whether growth factors, including IGF-1 and IGFBP3, mediate the relationship between improved nutritional provision and improved FFM gains, cognition, and speed of processing in preterm infants. Growth factors will be drawn at 1 week of age and 35 weeks PMA.

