Despite the potential benefits, early enhanced macronutrient provision to VLBW preterm infants is not routinely practiced due to concerns about intolerance and toxicity. These concerns are based on older trials using different nutritional products than those routinely used in NICU's today. More recent studies (mostly small and retrospective) have found that earlier introduction and more rapid advancement of lipids and protein are safe, and in fact may decrease the incidence of hyperglycemia and parenteral nutrition associated cholestasis. In addition, recent findings of increased adiposity among preterm infants at term CA has discouraged early enhanced nutrient provision based on a fear that this strategy, while being beneficial for the brain, will nonetheless lead to further increases in adiposity. However, our group and others have instead found that increased nutrition provision, both in calories and in protein, leads to increased FFM gains, without accompanying increases in FM or adiposity7.19. Work under Specific Aims 1 and 2 will address this uncertainty through a comprehensive examination of both neurodevelopmental and metabolic outcomes (i.e., body composition) in a randomized nutrition intervention trial.

> While the relationships between early malnutrition, poor growth and worsened neurodevelopment are relatively clear, the mechanisms behind these associations have vet to be elucidated. IGF-I is nutritionally regulated and negatively influenced by early malnutrition. Levels of IGF-1 play an important role in early postnatal growth, body composition and blood pressure in childhood, and improved neurodevelopmental outcomes among preterm infants. Circulating growth factor concentrations, like IGF-1, are therefore potential mediators of the effect of nutrition intervention on diverse preterm outcomes, which hypothesis we are testing in Specific Aim 3. If this hypothesis is supported, IGF-1 could then be used as a biomarker for prediction of later outcomes and, relatedly, as a tool for monitoring the success of early nutrition interventions. In the future, development of a nutritional intervention that optimizes IGF-1 levels early in life for preterm infants could indicate whether or not the proper balance is being struck between adequate early FFM gains to optimize neurodevelopment and minimizing excess FM gains to decrease long-term metabolic risk.

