### 4.0 Study Intervention

4.1 Description: This nutritional intervention is designed to accelerate the addition of macronutrients over the first week of life to minimize the period of malnutrition, and is based upon the findings of numerous smaller, less comprehensive studies and expert opinion. Once consent is obtained, and the infant is admitted to the NICU, enrolled infants will be randomized to either receive parenteral nutrition per the standard NICU parenteral nutrition protocol or via the enhanced nutrition protocol for the first week of life via random envelope selection. Stratified

block randomization will be performed. Infants will be stratified by gestational age (22-25, 26-29, 30-32 weeks). Within each stratum, permuted block randomization will ensure that study personal are unable to predict treatment allocation. Infants

randomized to the enhanced nutrition protocol will receive starter total parenteral nutrition (TPN) initiated at 80 mls/kg/day to provide protein at 4 grams/kg/day and a glucose infusion rate (GIR) of ~5.5 mgs/kg/min as soon as IV access has been obtained. Enhanced nutrition protocol infants will also be started on intralipids (IL) at 2 grams/kg/day once IV access is obtained. Infants randomized to the enhanced nutrition protocol will receive 4 grams/kg/day of protein throughout the first week of life. IL will be increased to 3 grams/kg/day on day of life (DOL) 2 and to 3.5 grams/kg/day on DOL 3. They will remain on this amount for at least the first week of life or until sufficient enteral feeding volumes have been established. GIR will be advanced by  $\sim 1.5 \text{ mgs/kg/min per day}$ throughout the first week of life to a maximum of 12-14 mgs/kg/min. Again, they will then remain on this amount until sufficient enteral feedings have been established (typically approximately 1-2 weeks). Infants randomized to the standard nutrition protocol will receive macronutrients per the caregivers discretion, most commonly initiated with starter TPN at 60 mls/kg/day giving 3 grams/kg/day of protein and a GIR of ~4 and IL provided at 0-1 gram/kg/day. Advancement is most typically by 1

mg/kg/min per day for GIR and 1 gram/kg/day per day for IL and protein in the standard NICU protocol. Pertinent aspects of the differences in nutritional treatment in intervention and control groups are summarized in the table below

	Day 1	Day 2	Day 3	Day 4	Day 5	Day 6	Day 7	
Control								
GIR	4.2	5	6	7	8	9	10	

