#### 9.0 Study Population

- 9.1 Inclusion Criteria: We will include VLBW (birth weight <1500grams) preterm (gestational age (GA) at birth < 32 weeks) infants admitted to the University of Minnesota Masonic Children's Hospital NICU, for which written informed consent can be secured from a parent within 12 hours of birth.
- 9.2 Exclusion Criteria: Infants who are diagnosed prenatally with a clinical condition (other than prematurity) that is known to affect growth rate, adiposity, or neurocognitive development, who experienced severe birth asphyxia, who are enrolled in another study affecting nutritional management, or who are likely to be transferred out of the NICU will be excluded from participation.
- 9.3 Screening: Admissions to the antepartum unit and to the NICU will be screened daily by the inpatient research coordinator for potential eligibility for the trial.

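### The Aim 3 IGF-1 predictor and mediator analyses specify no adjustment for gestational age or baseline illness, so if nutrition changes both IGF-1 and outcome, IGF-1 can pass as a mediator without being one

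*Combined protocol and SAP*

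**What the plan says.** Section 1.0 (Aim III) fixes the sampling times: "Growth factors will be drawn at 1 week of age and 35 weeks PMA". Section 5.2 gives the same two times, with the second as approximately 35 weeks CA. Strata start at 22 weeks (Section 4.1: "Infants will be stratified by gestational age (22-25, 26-29, 30-32 weeks") and eligibility ends below 32 weeks (Section 9.1: "preterm (gestational age (GA) at birth < 32 weeks) infants").

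Section 16.0, item 15.1, describes the primary models by assigned group. It then names GA at birth, birth z scores and degree of illness for additional, secondary models, with precision as the stated purpose. The Aim 3 text follows:

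- Predictor analysis: "IGF-1 levels at both 1 week and 35 weeks will be examined as predictors of later neurodevelopment and body composition outcomes". No covariates are listed.
- Mediator criterion 1: the intervention is significantly associated with IGF-1 and with outcomes.
- Mediator criterion 2: IGF-1 is significantly associated with FFM and neurodevelopmental outcomes. No covariates are listed, and group is not mentioned.
- Mediator criterion 3: the group effect is smaller "in a model that includes both IGF-1 and treatment group as predictors" than in the model without IGF-1.

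The paragraph ends by allowing other, unspecified explorations of IGF-1. Section 2.1 states the use of a positive result: if the mediator hypothesis is supported, "IGF-1 could then be used as a biomarker for prediction of later outcomes", and also as a tool for monitoring nutrition interventions.

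**The concern.** Randomisation protects the comparison of groups. It does not protect the association between IGF-1 and outcome, because nobody is randomised to an IGF-1 level. Birth GA and early illness are plausible common causes of low IGF-1 and poor outcome. Balancing GA between arms leaves that path open within each arm.

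The first sample makes the link with GA direct. At one week of age an infant's postmenstrual age (PMA) is birth GA plus one week, so the spread of birth GA carries straight into the measurement.

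Criterion 2 has a second weakness. If the intervention changes both IGF-1 and outcome by separate routes, the two are correlated in the pooled sample through treatment alone.

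The result would feed a biomarker statement and, through Section 15.2, the planning of a larger trial. A rule that often passes when IGF-1 does nothing is a poor basis for either.

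**Working it through.** **Inputs from the documents.** 40 infants per group; about 12% loss; two-sided 0.05; GA from 22 weeks to below 32 weeks. The sample-size figure reproduces: 40 × 0.88 = 35.2, so 35 per group and n = 70. The plan gives no power or effect size.

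**Age at sampling.** First sample: 22 + 1 = 23 weeks PMA, up to 31w6d + 1 week = 32w6d. Second sample: PMA is fixed near 35 weeks, while postnatal age runs from 35 − 31w6d (about 3 weeks) to 35 − 22 = 13 weeks.

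**Assumptions (none is in the documents).** GA has correlation a with IGF-1 and b with outcome. Treatment T shifts each by d SD. IGF-1 has no effect on outcome:

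- IGF-1 = d·T + a·GA + √(1−a²)·error
- outcome = d·T + b·GA + √(1−b²)·independent error

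One IGF-1 value and one outcome are analysed by ordinary least squares. Illness is not simulated.

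**Stand-alone predictor test, d = 0.** The crude correlation is a·b. By Fisher's approximation the rejection rate is Φ(z√67 − 1.96) + Φ(−z√67 − 1.96), with z = atanh(ab) and √67 = 8.185.

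- 0.2/0.2: ab = 0.04, z√67 = 0.33, rate 6%
- 0.3/0.3: ab = 0.09, z√67 = 0.74, rate 11%
- 0.4/0.4: ab = 0.16, z√67 = 1.32, rate 26%
- 0.5/0.5: ab = 0.25, z√67 = 2.09, rate 55%
- 0.6/0.5: ab = 0.30, z√67 = 2.53, rate 72%

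Simulation agrees (6%, 11%, 26–27%, 55–56%, 72–73%). With GA in the model the rate is about 5%.

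**Criterion 1 as a gate.** With d = 0 it needs two chance findings, and the full rule passes in at most 0.5% of runs, even at 0.7/0.5. With d = 0.7 the noncentrality is 0.7/√(2/35) = 2.93, so power is about Φ(2.93 − 1.96) = 0.83 for each effect. Both are significant in roughly 0.83² ≈ 0.69 of trials, so the gate is usually open.

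**Criterion 2 with d = 0.7.** With equal arms, treatment adds 0.25 × 0.49 = 0.1225 to the variances and the covariance, so r = (ab + 0.1225)/1.1225. At ab = 0, r = 0.109 and the test rejects in about 15% through treatment alone. At 0.6/0.5, r = 0.376 and it rejects in about 90%.

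**Criterion 3.** Any shrinkage counts. Simulated pass rates are about 50% with no GA confounding, 75% at 0.3/0.3 and 97% at 0.5/0.5.

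**Full rule, d = 0.7, simulated.**

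| GA correlations (IGF-1/outcome) | As written | GA and group in all models |
|---|---|---|
| 0/0 | about 12% | about 2% |
| 0.2/0.2 | about 20% | about 2% |
| 0.3/0.3 | about 28% | about 2% |
| 0.4/0.4 | about 44% | about 2% |
| 0.5/0.5 | about 60% | about 2% |
| 0.6/0.5 | about 65% | about 2% |

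Neither addition is enough alone. With group added to criterion 2 but no GA, the rule still passes in about 7% (0.3/0.3) to 38% (0.5/0.5). With GA but not group, the IGF-1 test still rejects in about 16% to 24% from 0.3/0.3 to 0.6/0.5.

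**The case against.** A reader might infer that IGF-1 could be declared a biomarker when it merely re-expresses immaturity. The documents do not support that. Section 2.1 makes the biomarker statement conditional on the mediator hypothesis, and criterion 1 requires an effect of randomised group on IGF-1 and on outcomes. Allocation is also stratified by GA. Immaturity alone therefore passes the full rule in under 1% of trials.

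A reader might also say that the plan leaves out GA and illness. That is too firm. Both are named for secondary models, and the open clause on other explorations could include adjustment. The accurate statement is that neither is specified for the Aim 3 IGF-1 analyses.

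Other points have weight:

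- The plan attaches no declaration to the stand-alone predictor test. A crude predictor can be real without being causal, so 5% is the benchmark only for the question of what IGF-1 adds beyond GA.
- Every correlation is assumed, and at 0.2/0.2 the predictor test barely exceeds 5%.
- Corrected-age testing and body composition z scores deal with age at measurement and may weaken the GA/outcome link, although they do not remove birth GA.
- The PMA spread at one week is birth GA under another name, not a separate defect.
- Aim 3 is a secondary, exploratory part of an 80-infant pilot, and its wording is hedged.

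These points narrow the concern. They do not answer the case in which treatment changes both IGF-1 and outcome, which is what Section 1.0 hypothesises.

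**Conclusion.** The concern holds in a limited form. As specified, the mediator rule protects well against a false declaration when the intervention does nothing, and poorly when it works by routes other than IGF-1. Under assumed 0.7 SD effects on both IGF-1 and outcome with n = 70, false passes run from about 12% with no GA confounding to about 65% at GA correlations of 0.6/0.5. Pre-specified adjustment for GA and group brings this to about 2%.

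The stand-alone predictor test has no treatment-effect gate. Through GA alone it is significant in about 6% (0.2/0.2) to 73% (0.6/0.5), so by itself it cannot show that IGF-1 adds to what is known at birth.

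The direction follows from the stated models. The size rests on correlations and effects that the documents do not give, and illness would need its own assumptions. The primary feasibility outcome is not affected.

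**What to change.** In Section 16.0, item 15.1:

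1. Include birth GA, SNAP on DOL 1 and treatment group in every model where IGF-1 or IGFBP3 predicts or mediates an outcome. This covers the criterion 2 test and both models compared in criterion 3. Use DOL 1 SNAP rather than DOL 7, because DOL 7 follows the start of the intervention and may be changed by it.
2. For the sample at about 35 weeks, add exact PMA at the draw if draw dates are recorded. The documents do not say that they are, so this needs confirming.
3. Report unadjusted IGF-1/outcome associations as descriptive only.
4. Base any biomarker statement on what IGF-1 adds beyond GA and illness.

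The cost is plan wording. GA and SNAP on DOL 1 are already collected under Section 5.2. The downside is two or three extra model terms with about 70 infants.
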